7. PLANNED ANALYSIS

The format of the listings and tables will follow the BI guideline "Standards for Reporting of Clinical Trials and Project Summaries" (3).

Disposition of the patient population participating in the trial will be summarized by the presentation of the frequency of patients screened, randomized, screened but not randomized, randomised and treated, randomized but not treated, who completed the treatment period as planned, who were prematurely discontinued study treatment by reason, who is still ongoing in the study, who completed the observational period as planned, who prematurely discontinued study participation, and who completed Week 8 visit (V7).

[figure not shown]
A frequency of patients with iPDs will be presented by treatment group for treated set. The frequency of patients in different analysis sets will also be presented for each treatment group. The iPDs per patient will be listed indicating whether the iPD led to exclusion from patient sets analysed.

For in-text tables presenting descriptive analysis of the endpoints and other variables (in original scale), the set of summary statistics is: N (number of patients with non-missing values), mean, standard deviation (SD).

For end-of-text tables, the set of summary statistics is: N (number of patients with non-missing values) / Mean / SD / Min / Q1 (lower quartile) / Median / Q3 (upper quartile) / Max.

Statistical parameters will be displayed to a defined number of decimal places as specified in the BI guideline "Reporting of Clinical Trials and Project Summaries" (3).

Tabulations of frequencies for categorical data will include all possible categories and will display the number of observations in a category as well as percentage (%) relative to the respective treatment group. Percentages will be based on all patients in the respective patient set whether they have non-missing values or not. Percentages will be rounded to one decimal place. The category missing will be displayed if and only if there are actual missing values.

7.1 DEMOGRAPHIC AND OTHER BASELINE CHARACTERISTICS

Only descriptive statistics are planned for this section.

Descriptive statistics for demographic parameters and baseline characteristics will be presented based on the RS. A separate listing will be provided for gastroscopy data.

For the continuous variables described below, categories are defined in Table [7.1:1](#). These variables will be presented according to the number and percentage of patients in each category, in addition to the display of the summary statistics for continuous variables.

Table 7.1: 1 Categories for summary of continuous variables

Variable	Categories
Age (years)	< 50 50 to < 65 65 to ≤ 75 > 75
	< 65 ≥ 65
Weight (kg)	≤ 70 > 70 to ≤ 80 > 80 to ≤ 90 > 90
BMI (kg/m ²)	< 25 25 to < 30 ≥ 30
eGFR	≤ 30 > 30 to ≤ 45 > 45 to ≤ 60 > 60 to ≤ 90 > 90
Time since first diagnosis of cirrhosis (years)	≤ 1 > 1 to ≤ 5 > 5 to ≤ 10 > 10
Baseline HVPG (mmHg)	≤ 12 > 12 ≤ 15 > 15

7.2 CONCOMITANT DISEASES AND MEDICATION

Only descriptive statistics are planned for this section of the report. Analyses of the concomitant diseases and medication as well as non-drug therapies will be based on RS.

Concomitant diseases will be coded according to the most recent version of Medical Dictionary for Drug Regulatory Activities (MedDRA).

Concomitant medication will be coded according to the most recent version of the World Health Organization – Drug Dictionary (WHO-DD).

A medication will be considered concomitant to treatment if it:

- is ongoing at the start of trial medication intake.
- starts within the on-treatment period (see Section [6.1](#) for a definition of study analysis phases).

Concomitant medication use will be summarized with frequency and percentage of patients by Anatomical Therapeutic Chemical 3 (ATC3) class and preferred name.

7.3 TREATMENT COMPLIANCE

Only descriptive statistics are planned for this section of the report.

The compliance based on TS will be described as collected in the eCRF. Number and percentage of patients with compliance in following categories will be displayed at each visit since week 1:

- “Yes”,
- “No” and,
- “Missing”.

7.4 PRIMARY OBJECTIVE ANALYSIS

7.4.1 Main analysis

The primary endpoint will be analysed through a MMRM model in combination with the primary estimand of handling ICEs (see [Section 6.3](#)). The FAS will be used for the analysis: the patient set includes all patients who had at least one evaluable baseline HVPG measurement. The missing data will not be imputed. Instead, the MMRM will handle missing data based on a likelihood method under the “missing at random” assumption.

For the MMRM model, treatment at each visit, use of NSBBs or carvedilol (yes / no) at baseline, and baseline HVPG at each visit will be used as covariates. Refer to Section 7.2.3 of the CTP for a detailed description of the statistical analysis for the percentage change from baseline in HVPG after 24 weeks of trial treatment.

The adjusted estimate of mean percentage change from baseline in HVPG at 24 weeks and its standard error will be obtained from MMRM for the placebo and treatment groups. The 95% CI will be provided for adjusted mean effect of each treatment group as well as the comparison with placebo.

SAS code for **the MMRM model** will be based on the following structure:

```
PROC MIXED DATA=alldat cl method=reml;  
  CLASS visit trt subject;  
  MODEL chg = base*visit visit*trt stra / ddfm=kr s CL; REPEATED visit / subject=  
  subject type=un r rcorr;
```

```
LSMEANS visit*trt /pdiff=all om cl alpha=0.05 slice=visit;
```

```
RUN;
```

7.5 SECONDARY OBJECTIVE ANALYSIS

7.5.1 Key secondary objective analysis

This section is not applicable as no key secondary endpoints have been specified in the protocol.

7.5.2 Secondary objective analysis

The secondary endpoints for this study are described in CTP Section 2.1.3.

For the secondary endpoint of percentage change in HVPG after 8 weeks of treatment, the analysis of covariance (ANCOVA) will be used. The analysis will be performed on the FAS with treatment assignment as randomized and include on-treatment HVPG only. If a patient misses the Week 8 visit, the missing data will not be imputed.

This model will include treatment and use (or not) of NSBBs or carvedilol as fixed classification effects and baseline HVPG as a linear covariate. The random error is assumed to be normally distributed with mean 0 and variance σ^2 . The analysis will only be used for estimation of treatment effects without performing statistical tests.

For other secondary endpoints, only descriptive statistics will be presented.

For the occurrence of decompensation events, categories are defined in Table [7.5.2:1](#)

Table 7.5.2:1 Categories for decompensation events

Categories	Definition
Ascites	PT - 'Ascites' PT - 'Bacterascites' PT - 'Haemorrhagic ascites'
Variceal haemorrhage	PT - 'Oesophageal varices haemorrhage' PT - 'Oesophageal haemorrhage' PT - 'Bleeding varicose vein' HLT - 'Gastric and oesophageal haemorrhages' HLT - 'Non-site-specific gastrointestinal haemorrhages'
Hepatic encephalopathy	PT - 'Hepatic encephalopathy' PT - 'Coma hepatic' PT - 'Hyperammonaemic encephalopathy' PT - 'Hyperammonaemic crisis'
Other	PT - 'Cardiohepatic syndrome' PT - 'Hepatorenal syndrome' PT - 'Hepatorenal failure' PT - 'Hepatic hydrothorax' PT - 'Hepatopulmonary syndrome'

7.7 EXTENT OF EXPOSURE

A descriptive statistics table with mean, SD, median and range of the number of days a patient was on treatment will be provided for the treated set. The tables will also provide the sum total of the time (in years) that all patients pooled together were on treatment. A separate listing will be created for patients who switched treatment at any time (i.e., down-titration) indicating exposure to each treatment.

A frequency table of number and percent of patients belonging to each categorical range of exposure weeks will be provided as well. The following are the categories of exposure-ranges (in weeks):

>0 to 4 weeks, >4 to 8 weeks, >8 to 12 weeks, >12 to 18 weeks, >18 to 24 weeks, >24 weeks.

No temporary treatment interruption period will be reported.

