Following randomisation patients will begin the intake of trial medication and will enter a dose-titration period. All patients in all treatment groups will start this period on a dose of ██████████ *BID* 685509 or matching placebo. If the dose is tolerated one week later (at Visit 3, day 8), the dose for all treatment groups will be up-titrated to ██████████ *BID* 685509 or matching placebo. For the ██████████ *BID* dose treatment group only, and if the dose is tolerated, a second up-titration to ██████████ *D* 685509 or matching placebo will occur after another week (at Visit 4, day 15). However, as this is a double-blind trial, patients randomised both to ██████████ *BID* 685509 and to placebo will also have a dose-titration at Visit 4 (day 15). For these treatment groups the dose-titration will be a pseudo-titration (i.e. those randomised to ██████████ *BID* BI 685509 will remain on that dose, and those randomised to placebo will remain on placebo). Following the dose-titration period, and if the dose is tolerated, patients will remain on their maximum planned maintenance dose for the remainder of the treatment period until they reach the End of Treatment (EoT) visit and 24 weeks of treatment. If the dose is not tolerated, trial medication may be interrupted or the dose can be reduced / down-titrated.

The ultrasound and ██████████ of the liver and spleen, and the HVPG measurement will be repeated during the randomised treatment period (refer to Figure [3.1: 1](#)).

After approximately 60 randomised patients have completed Visit 7 (week 8 of treatment) and the HVPG procedure, there will be an interim analysis. Recruitment will continue whilst the analysis takes place. The results of the interim analysis will establish short-term efficacy and allow assessment of an internal development milestone. For further details regarding the interim analysis refer to Section [7.2.8](#).

After the 24 week randomised treatment period all patients will enter a 4 week follow-up period without trial medication. The patient's participation in the trial will be complete when they have performed the last planned visit (i.e. End of Study [EoS], 4 weeks after EoT).

[figure not shown]

Figure 3.1: 1 Trial design schematic

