4.1.4 Drug assignment and administration of doses for each patient

Trial medication will be dispensed at the investigational sites in accordance with the [Flow Chart](#). At dispensing visits patients will be given the appropriate number of medication kits (range 1-4) depending on the interval between the visits (for further kit details refer to Section [4.1.6](#)). The last dose of trial medication will be administered in the evening of the day before the EoT visit.

All patients, regardless of the treatment group they are assigned to, will start at Visit 2 on a dose of ■■■■ BI 685509 BID or matching placebo. At Visit 3, 7 days later, and again at Visit 4, a further 7 days after Visit 3, all patients will either be up-titrated or pseudo up-titrated first to a dose of ■■■■ BI 685509 BID or matching placebo, and then to a dose of ■■■■ BI 685509 BID or matching placebo. Pseudo up-titration will be used at a visit instead of a true up-titration when the maximum planned maintenance dose for a treatment group has been reached; in this way the blind across treatment groups will be maintained (refer to Table [4.1.4: 1](#)). Patients will be informed about the dose titration period and will be made aware that up-titration or pseudo-titration is being used. If a patient does not tolerate an up-titration, e.g. due to orthostatic dysregulation, the rules in Section [4.1.4.1](#) must be followed. From Visit 4 onwards, patients will continue to receive the maximum planned maintenance dose for the treatment group they are assigned to (unless a down-titration is required), until reaching the EoT visit 24 weeks after starting the trial medication.

If a patient has an AE that, based on Investigator judgement, may be related to trial medication, the trial medication can either be:

- interrupted (i.e. the trial medication is stopped, and subsequently re-started by following the up-titration approach described above)

OR

- the dose can be reduced (down-titrated) if the patient has successfully completed the dose titration period (i.e. Visit 4)

For further details refer to Sections [4.1.4.1](#) and [4.1.4.2](#).

All trial medication assignments, including up / down-titrations and provision of replacement kits, will be managed through the IRT system. Down-titrations must not be performed by instructing the patient to take less than the two daily doses (refer to Section [4.1.4.1](#)).

Table 4.1.4: 1 Drug assignment and dosage by treatment group

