4.3 TREATMENT COMPLIANCE

Patients are requested to bring all remaining trial medication including empty package material with them when attending visits.

Based on tablet counts, treatment compliance will be calculated as shown in the formula below. Compliance will be verified by the CRA authorised by the Sponsor or delegate.

$$\text{Treatment compliance (\%)} = \frac{\text{Number of tablets actually taken}}{\text{Number of tablets which should have been taken as directed by the Investigator}} \times 100$$

If the number of doses taken is not between 80-120%, site staff will explain to the patient the importance of treatment compliance.

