7.8.1.2 Analysis of other significant AEs

Other significant AEs will be reported and summarized according to ICH E3 criterion [\(5\)](#). Thus, AEs classified as ‘other significant’ will include those non-serious adverse events with ‘action taken = discontinuation’ or ‘action taken = dose reduced’.

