7.8.1.3 AE summaries

An overall summary of AEs will be presented.

The frequency of patients with AEs will be summarized by treatment, primary SOC and PT. AEs which were defined as secondary endpoints will be summarized separately. AEs will also be reported by intensity according to the maximum Common Terminology Criteria for Adverse Events (CTCAE). Separate tables will be provided for patients with other significant AEs according to ICH E3 [\(5\)](#), adverse events of special interest (AESI), for patients with serious adverse events, for patients with AEs leading to dose reduction, for patients with AEs leading to discontinuation, and for patients with drug-related AEs.

The SOC will be sorted alphabetically, PTs will be sorted by frequency (within SOC). Customized sorting orders may also be used based on trial needs, e.g., SOC sorted by frequency.

For further details on summarization of AE data, please refer to “Handling of missing and incomplete AE dates” [\(2\)](#) and “Analysis and Presentation of Adverse Event data from Clinical Trials” [\(6\)](#).

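### The SAP reports dose reductions and discontinuations but excludes temporary interruption with re-titration, which before Visit 4 is the only dose change for an adverse event short of stopping the drug for good

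*SAP*

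**What the plan says.** **Protocol.** Section 3.1 says that if a dose is not tolerated, "trial medication may be interrupted or the dose can be reduced / down-titrated". Section 4.1.4 gives two options for an AE that may be related to the drug. The drug can be "interrupted (i.e. the trial medication is stopped, and subsequently re-started by following the up-titration approach described above", or the dose can be reduced once the titration period has been completed at Visit 4. Section 4.1.4.1 bars down-titration before Visit 4 and requires permanent discontinuation at that stage if AEs are persistent or effects severe. Section 4.1.4.2 returns any patient who misses more than 3 consecutive doses to the starting dose, with at least 7 consecutive days on each step before the next. Section 4.2.2.1 separately requires a temporary stop during short-term use of a drug with known Torsade de Pointes risk.

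**SAP.** Section 7.7 summarises days on treatment, lists patients who switched treatment (defined as down-titration), and adds: "No temporary treatment interruption period will be reported". Section 7.8.1.2 counts a non-serious AE as otherwise significant if the action taken was discontinuation or "action taken = dose reduced". Section 7.8.1.3 plans separate tables "for patients with AEs leading to dose reduction, for patients with AEs leading to discontinuation". No visible section plans a table or listing of interruptions, of AEs leading to interruption, or of re-titrations.

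**The concern.** Tolerability is part of the stated objectives (Protocol 2.1.1). Protocol 3.2 describes orthostatic dysregulation as dose-limiting and gives improved tolerability as the reason for titrating. Protocol 1.2.3 reports that orthostatic intolerance in the higher dose groups of the earlier hepatic-impairment trial did not lead to discontinuation. A discontinuation table alone may therefore miss this kind of problem.

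Anyone using this trial to judge the two regimens for Phase III would want to know, by arm, how often an AE stopped the drug and sent the patient back to the first step, and for how long. For AEs managed in the first two weeks, the dose-reduction table cannot supply this, because reduction is not allowed then. The exposure summary gives no deduction for days off drug.

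**Working it through.** The plan gives no figure to reproduce. The check compares the permitted actions with the planned outputs, then sizes one interruption from the protocol's own rules.

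**1. Permitted actions against planned outputs**

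| Response to a possibly related AE | Before Visit 4 | From Visit 4 | SAP output |
|---|---|---|---|
| Interrupt, then re-titrate | allowed | allowed | none; periods excluded by SAP 7.7 |
| Reduce dose | barred | allowed | listing (7.7), AE table (7.8.1.3) |
| Discontinue | allowed; required if AE persistent or effects severe | allowed | disposition (7), AE table (7.8.1.3) |

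Protocol 4.1.4.2 also lets a patient be held at the current step at Visit 3 or 4. That follows from missed doses and the 7-day rule and is not a separate response to an AE.

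**2. Could another output recover the information?**

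- *Disposition* (SAP 7) counts patients "who completed the treatment period as planned, who were prematurely discontinued study treatment by reason". An interrupted patient who resumes counts as neither discontinued nor otherwise marked.
- *Exposure* (SAP 7.7) states no deduction. The on-treatment phase in SAP 6.1 runs from first administration to last intake plus a fixed number of days, with no gap for an interruption.
- *Compliance* (SAP 7.3): "Number and percentage of patients with compliance in following categories will be displayed at each visit since week 1", namely Yes, No or Missing. The denominator in Protocol 4.3 is "Number of tablets which should have been taken as directed by the Investigator". If doses held on instruction leave that denominator, a directed hold gives 100%. At 4 tablets a day, a 2-day hold gives (14 − 2) × 4 = 48 of 48 tablets over 14 days, and (28 − 2) × 4 = 104 of 104 over 28 days. If held doses are instead counted as missed, the results are 48/56 = 85.7% and 104/112 = 92.9%, both inside the protocol's 80–120% range. In a 7-day titration interval the same hold would give 20/28 = 71.4%, outside the range. It would then look like ordinary non-compliance, with no link to an AE or a re-start.

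**3. Cost of one interruption to one patient**

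Inputs: more than 3 doses means at least 4, which is 2 days at two doses a day (4.1.4.2). Each step lasts at least 7 days (4.1.4.2). There is one step up to maintenance in the low-dose arm and two in the high-dose arm (3.1). Treatment lasts 24 weeks, or 168 days.

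*After maintenance is reached:*

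- Low dose: 2 + 7 = 9 days; 9/168 = 5.4%.
- High dose: 2 + 7 + 7 = 16 days; 16/168 = 9.5%.

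*During titration,* with first missed day d and 2 days off, the patient restarts on day d + 2:

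- Low dose: maintenance is reached on day d + 9 instead of Day 8, a loss of d + 1 days. For d = 2 to 7 that is 3 to 8 days (1.8% to 4.8% of 168).
- High dose: maintenance is reached on day d + 16 instead of Day 15, again a loss of d + 1 days. For d = 2 to 14 that is 3 to 15 days (1.8% to 8.9%).

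These are minimums: longer holds, or waiting for a visit at which to step up, add days.

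**The case against.** The strongest reply is that this is a disclosed reporting choice in a descriptive trial. No hypothesis is tested, interruption is not an endpoint, and Protocol 7.2.6 promises no interruption table, so the SAP does not contradict the protocol. The chosen tolerability endpoints are grade 3 or higher hypotension or syncope, and discontinuation due to either, at 8 and 24 weeks. All are reported, and SAP 7.8.1.5 adds patient-based and event-based summaries of hypotension and syncope. This stands, and it limits the weight of the point.

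It also stands that the gap before Visit 4 is narrower than it may first look. Persistent AEs or severe effects in that period must lead to discontinuation, which is tabulated. What goes unseen is the AE that was neither persistent nor severe and was managed by a hold.

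Safety outputs also follow sponsor standards that are cited but not available here, and the sentence in SAP 7.7 concerns interruption periods. AE listings may still show the action taken. That is possible, but no stated output summarises it by arm.

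Four stronger readings are tempting and are not supported:

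- *That AEs during titration disappear from the report.* They remain in the general, intensity and drug-related summaries.
- *That 9 or 16 days is the minimum for any interruption.* It applies only once maintenance is reached. Earlier, some of the days below maintenance were planned anyway.
- *That the 5–7 days in Protocol 3.3.4.1 is a typical hold.* It is the length of an antibiotic course, not of a stop in trial drug.
- *That Protocol 4.1.4.1 forces down-titration for every related AE.* That section sets the rules for down-titration, and 4.1.4 offers interruption as the alternative.

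**Conclusion.** The point holds as a limited reporting gap. The SAP expressly leaves out one of the protocol's two dose changes for AEs short of discontinuation, and before Visit 4 the only one. No other visible output shows its frequency, reason or duration by arm, and no deduction of off-drug days from exposure is stated.

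Per affected patient, the minimum time off drug or below the assigned dose is 9 days (low dose) or 16 days (high dose) after maintenance, and 3 to 8 or 3 to 15 days during titration. These figures assume the shortest interruption that triggers re-titration and step-ups at the earliest permitted time. The size across the trial cannot be given, because the documents state no interruption rate.

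A reader might infer that the efficacy result is compromised. This point does not support that: the missing outputs are descriptive and feed no term of the primary HVPG model. The change is worth making because it is cheap and bears on a stated objective.

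**What to change.** **SAP 7.7.** Delete the sentence excluding interruption periods. Report by arm on the treated set, as far as eCRF and IRT data allow:

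- patients with at least one interruption of more than 3 consecutive doses, split by start before or from Visit 4;
- the reason for interruption;
- days off drug;
- the number of re-starts of titration;
- days on treatment net of off-drug days.

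**SAP 7.8.1.3.** Add a table of AEs leading to drug interruption, and one combined table of AEs leading to interruption or dose reduction with each patient counted once.

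**Cost.** A few extra descriptive tables. There is no multiplicity cost, since nothing is tested, and both changes remain possible after dosing has ended. The fix depends on interruption dates and an action-taken category for interruption having been captured, which the documents do not confirm. Protocol 4.1.4 routes all medication assignments through the IRT, and SAP 7.8.1.1 already plans drug-related AEs by treatment actually taken at each time point. If dates are lacking, re-starts should still be countable from the IRT, but days off drug would not be.
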